8.7.1 Efficacy Interim Analyses

A summary of interim and final analyses strategy for efficacy is provided in [Table 27](#).

Table 27 Summary of Interim and Final Analyses Strategy for Efficacy

Analyses	Key Endpoints	Timing [†]	Estimated Months after First Subject Randomized	Primary Purpose of Analysis
Efficacy IA	
 • EFS • OS 	At least 353 EFS events have been observed and all subjects have been followed up for at least 23 months	~48 months	
 • Demonstrate EFS superiority • Evaluate OS superiority
Efficacy FA	
 • EFS • OS 	At least 410 EFS events have been observed and all subjects have been followed up for at least 35 months	~60 months	
 • Demonstrate EFS superiority (if not significant at IA) • Evaluate OS superiority

EFS = event-free survival; FA = final analysis; IA = interim analysis; OS = overall survival.

[†] Note: For efficacy IA and FA, if the EFS events accrue slower than expected, the analysis can be delayed up to 3 months after the projected timing, i.e., the Sponsor may conduct IA and FA with additional 3 months of follow-up, or the specified number of events is observed, whichever occurs first.

Decisions to stop the study early will be based on eDMC recommendations with review by the Executive Oversight Committee. In the event that the study is stopped early for efficacy, the study will continue to follow subjects for survival update.

Type I error control for the efficacy analyses as well as efficacy bounds are described in Section 8.8 - Multiplicity.

8.7.2 Safety Interim Analyses

A summary of interim analysis strategy for safety is provided in [Table 28](#).

Table 28 Summary of Interim Analyses Strategy for Safety

Key Endpoints	Timing	Estimated Months after First Subject Randomized	Primary Purpose of Analysis
AEs	
 • First 30 subjects have completed Treatment 1 (concurrent CRT) phase • Every 4 months after the first planned safety IA for 1 year • Every 6 months thereafter and/or at the appropriate frequency as outlined by the eDMC. Details will be included in the DMC charter. 	
 • ~5 months • ~9, 13 months • ~19, 25, etc. (every 6 months and/or at the appropriate frequency as specified in the DMC charter) 	Safety evaluation

AE=Adverse Event; CRT=Chemoradiation therapy; DMC=Data Monitoring Committee; eDMC=external DMC; IA=interim analysis.

[figure not shown]
8.8 Multiplicity

8.8.1 Multiplicity Control for Efficacy Analyses

The overall Type I error for testing the EFS and OS hypotheses is strongly controlled at $\alpha=2.5\%$ (1-sided) by using a fixed sequential testing procedure in the order of EFS and OS. If the statistical criterion for success in the primary EFS hypothesis is met at the interim analysis or final analysis, the secondary OS hypothesis will be tested in all subjects.

Figure 3 shows the initial one-sided α -allocation for each hypothesis in the ellipse representing the hypothesis. The weight for reallocation from the EFS hypothesis to OS is represented in the box on the line connecting hypotheses. This is further explained below.

Figure 3 Multiplicity Schema

Event-Free Survival

The EFS hypothesis will be tested at $\alpha = 0.025$. Table 29 below shows the bounds and boundary properties for each analysis of EFS which were derived using a Lan-DeMets O'Brien-Fleming alpha-spending function. Note that the final row of the table indicates the total power to reject the null hypothesis. Also, note that the bounds and nominal alpha levels provided in Table 29 are based on the assumption that the number of EFS events at IA and FA are 353 and 410, respectively. At the time of IA, the observed number of events may differ substantially from the expected. To avoid overspending at the IA and leave reasonable alpha for the FA, the minimum alpha spending strategy will be adopted. At the IA, the information fraction used in Lan-DeMets spending function to determine the alpha spending at the IA will be based on the minimum of the expected information fraction and the actual information fraction at the time of the analysis. Specifically,

- In the scenario that the event accumulation is faster than expected, i.e., if the number of observed events exceeds the pre-specified number of events at IA, then the information fraction will be calculated as the pre-specified number of events at IA over the target number of events at FA, and hence the alpha spending at IA will not exceed the pre-specified level based on the pre-specified number of events, as shown in the table below.
- In the scenario that the event accumulation is slower than expected and the number of events is less than the pre-specified number of events in the table when IA is conducted, the bounds will be adjusted using the spending functions accordingly, with information fraction calculated as the actual number of events at IA over the target number of events at FA.

The final EFS analysis will use the remaining Type I error not spent at an earlier analysis, regardless of the number of events observed at the final analysis. The nominal alpha level at the final analysis will be calculated by considering the correlation between the test statistics, as determined by the actual number of EFS events at IA and FA.

If the EFS hypothesis is rejected at any analysis, the $\alpha = 0.025$ (one-sided) will be rolled over to the OS test.

Table 29 Efficacy Boundaries and Properties for EFS Analyses

Analysis [†]	Value	Efficacy
IA: 86%	Z	2.1517
N: 780	p (1-sided)	0.0157
Events: 353	~HR at bound	0.7952
Month: 48	P(Cross) if HR=1	0.0157
	P(Cross) if HR=0.7	0.8841
Final Analysis	Z	2.0422
N: 780	p (1-sided)	0.0206
Events: 410	~HR at bound	0.8172
Month: 60	P(Cross) if HR=1	0.0250
	P(Cross) if HR=0.7	0.9463

EFS=event-free survival; HR=hazard ratio; IA=interim analysis

[†]This column displays the number (Events) and percentage (%) of needed EFS events, the expected sample size (N) and the estimated months (Month) after first subject is randomized for each analysis.

p (1-sided): nominal α for group sequential testing.

~HR at bound: the approximate hazard ratio required to reach an efficacy bound.

P(Cross if HR=1): the probability of crossing a bound under the null hypothesis.

P(Cross if HR=0.7): the probability of crossing a bound under the alternative hypothesis.

Of note, while the information fraction used for alpha spending calculation will be the minimum of the actual information fraction and the expected information fraction, the correlations required for deriving the bounds will still be computed using the actual information fraction based on the observed number of events at the IA over the target number of events at FA.

The minimum spending approach assumes timing is not based on any observed Z-value and thus the Z test statistics used for testing conditioned on timing are multivariate normal. Given the probabilities derived with the proposed spending method, the correlations based on actual event counts are used to compute bounds that control the Type I error at the specified alpha level for a given hypothesis conditioned on the interim analysis timing. Since this is true regardless of what is conditioned on, the overall Type I error for a given hypothesis unconditionally is controlled at the specified level. By using more conservative spending early in the study, power can be retained to detect situations where the treatment effect may be delayed.

Overall Survival

Overall survival will be tested only if EFS superiority is demonstrated and will be tested at $\alpha = 0.025$. [Table 30](#) below shows the bounds and boundary properties for OS testing which were derived using a Lan-DeMets O'Brien-Fleming alpha spending function. Note that the bounds and nominal alpha levels provided in [Table 30](#) are based on the assumption that the number of OS events at IA and FA are 220 and 268, respectively. If the actual number of events at the OS analyses differs from those specified in the table, the same minimum spending approach as used for EFS will be implemented and the bounds will be adjusted accordingly. The final OS analysis will occur at the same time as the final EFS analysis, and the final OS analysis will use the remaining Type I error not spent at an earlier analysis, regardless of the number of events observed at the final analysis.

Table 30 Efficacy Boundaries and Properties for OS Analyses

Analysis [†]	Value	Efficacy
IA: 82%	Z	2.2169
N: 780	p (1-sided)	0.0133
Events: 220	~HR at bound	0.7412
Month: 48	P(Cross) if HR=1	0.0133
	P(Cross) if HR=0.71	0.6239
Final Analysis	Z	2.0305
N: 780	p (1-sided)	0.0212
Events: 268	~HR at bound	0.78
Month: 60	P(Cross) if HR=1	0.025
	P(Cross) if HR=0.71	0.79

HR=hazard ratio; IA=interim analysis; OS=overall survival.
† This column displays the number (Events) and percentage (%) of needed OS events, the expected sample size (N) and the estimated months (Month) after first subject is randomized for each analysis.
p (1-sided): nominal α for group sequential testing.
~HR at bound: the approximate hazard ratio required to reach an efficacy bound.
P(Cross if HR=1): the probability of crossing a bound under the null hypothesis.
P(Cross if HR=0.71): the probability of crossing a bound under the alternative hypothesis.

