7.1.4.2 FDG-PET

During screening, an FDG-PET or FDG-PET/CT scan should be acquired within 6 weeks of randomization. Then, at 12 weeks post-CRT ± 1 week (approximately Week 19 or Week 20) an FDG-PET or FDG-PET/CT scan should be acquired as part of neck management (see [Figure 2](#), See Section 7.1.2.10). The timing of the FDG-PET or FDG-PET/CT scan should be such that the neck dissection could be performed approximately 16-20 weeks post-CRT, if indicated.

The FDG-PET/CT may replace the CT/MRI scan if the CT is of diagnostic quality when this is the local standard practice.

All FDG-PET or FDG-PET/CT and corresponding CT/MRI imaging reports obtained during screening and on-study for all randomized subjects who have completed at least one post-baseline FDG-PET or FDG-PET/CT scan will be collected by the Sponsor as required by the regulatory agency. Since completion of the final efficacy analysis, any additional post-baseline FDG-PET or FDG-PET/CT reports are no longer required to be collected by the Sponsor.

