Interim Analyses	
Efficacy
 
One interim efficacy analysis will be performed in this study. Results will be reviewed by an external data monitoring committee (eDMC). The interim and final analysis timing and purpose is summarized below. Details are provided in Section 8.7.
 
• IA
○ Timing: at least 353 EFS events and all subjects have been followed up for at least 23 months (~86% of the final required EFS events, estimated to be 48 months after study start).○ Testing: Inferential analyses of EFS will be provided.• FA
○ Timing: at least 410 EFS events and all subjects have been followed up for at least 35 months (estimated to be 60 months after study start).○ Testing: Inferential analyses of EFS will be provided. 
Note that if the EFS events accrue slower than expected, the analysis can be delayed up to 3 months after the projected timing, i.e., the Sponsor may conduct the IA and FA with additional 3 months of follow-up, or the specified number of events is observed, whichever occurs first.
 
Safety
 
One interim safety analysis will be performed when the first 30 subjects have completed CRT. The eDMC will also review safety data periodically in the study.

Multiplicity	The Type I error rate for the EFS and OS hypotheses is strongly controlled at 2.5% (1-sided). A group sequential approach will be used to allocate alpha between the interim and final analyses of EFS. The study will be considered a success if EFS in all subjects is demonstrated to be statistically significant under multiplicity control.
Sample Size and Power	The planned sample size is approximately 780 subjects. For EFS, the trial has 94.6% power to demonstrate that pembrolizumab in combination with CRT is superior to placebo in combination with CRT at an overall one-sided 2.5% alpha-level, if the true hazard ratio is 0.7.

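### Section 8.8.1 gives two different rules for the interim–final correlation, and the one that divides by the target number of final events is wrong whenever the final EFS count is not 410

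*Combined protocol and SAP*

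**What the plan says.** Three statements in section 8.8.1 concern the correlation between the interim (IA) and final (FA) test statistics.

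- The paragraph on the final EFS analysis derives the nominal alpha from the correlation "as determined by the actual number of EFS events at IA and FA".
- The note after Table 29 says that, although spending uses the smaller of the actual and expected information fractions, the correlations for deriving the bounds are "computed using the actual information fraction based on the observed number of events at the IA over the target number of events at FA".
- The type I error argument after that note says "the correlations based on actual event counts are used to compute bounds that control the Type I error at the specified alpha level".

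The final count is not fixed at 410. Table 27 in section 8.7.1 sets the trigger as "At least 410 EFS events have been observed and all subjects have been followed up for at least 35 months", and its footnote adds that "if the EFS events accrue slower than expected, the analysis can be delayed up to 3 months after the projected timing". All remaining alpha is used at the final analysis whatever the event count. For OS, whose target is 268 deaths, "the same minimum spending approach as used for EFS will be implemented and the bounds will be adjusted accordingly".

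**The concern.** The interim bound follows directly from the alpha spent at that look and needs no correlation. In a two-look design the note can therefore act only on the final bound, which is where the other two statements say something else.

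The correlation of log-rank statistics at two looks is the square root of the ratio of events actually in the data. Putting the target in the denominator misstates it in either direction. With more than 410 final events the assumed correlation is too high, the bound is too lenient and type I error exceeds 2.5%. With fewer, the test is conservative. If interim events reach 410 the ratio is 1 or more and no valid final bound exists.

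At stake is the claim of strong control for the primary endpoint. A final p-value falling between the two thresholds would succeed under one sentence and fail under another.

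**Working it through.** **Inputs.** Sections 8.1, 8.8.1 and 8.9: one-sided alpha 0.025; Lan-DeMets O'Brien-Fleming spending; 353 and 410 planned EFS events; 780 subjects randomized 1:1; control EFS 70% at 12 months and 40% at 36 months (piecewise exponential); the stated 25-month accrual; 10% dropout at 12 months; looks at months 48 and 60.

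**Formulas.**

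- Interim spending: α₁ = 2[1 − Φ(2.2414/√t)], with t = min(353, IA events)/410.
- Interim bound: b₁ = Φ⁻¹(1 − α₁).
- Final bound b₂: solve P(Z₁ < b₁, Z₂ ≥ b₂) = 0.025 − α₁ under a bivariate normal with correlation ρ.
- Actual-count rule: ρ = √(IA/FA). Note's rule: ρ = √(IA/410).
- True type I error: α₁ + P(Z₁ < b₁, Z₂ ≥ b₂), evaluated at ρ = √(IA/FA).
- Hazard ratio at the bound: exp(−2b₂/√FA).

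**Step 1: reproduce Table 29.** t = 353/410 = 0.861 gives α₁ = 0.0157 and b₁ = 2.1517. With ρ = √0.861 = 0.928, b₂ = 2.0422 (p = 0.0206). Both bounds match the table. The event model gives 353.7 and 410.1 expected events at a hazard ratio of 0.7, matching the planned 353 and 410.

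**Step 2: counts under the null.** The planned counts assume a hazard ratio of 0.7. Type I error is evaluated at 1, where events accrue faster. The same accrual, dropout and control EFS then give about 397 events at month 48 and 456 at month 60.

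**Step 3: final bound at 397/456.** α₁ stays at 0.0157 because spending is capped at 353/410.

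| Rule | ρ | Final Z | Final p | HR at bound | Overall alpha |
|---|---|---|---|---|---|
| Actual counts | √(397/456) = 0.933 | 2.036 | 0.0209 | 0.826 | 2.50% |
| Note after Table 29 | √(397/410) = 0.984 | 1.972 | 0.0243 | 0.831 | 2.77% |

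**Step 4: interim held at 353, final count varied (illustrative).** The note gives p = 0.0206 in every row.

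| FA events | Correct final p | Overall alpha under the note |
|---|---|---|
| 370 | 0.0238 | 2.24% |
| 390 | 0.0220 | 2.39% |
| 410 | 0.0206 | 2.50% |
| 430 | 0.0194 | 2.59% |
| 450 | 0.0185 | 2.66% |

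**Step 5: sensitivity to the control rate.** Null hazards in both arms were multiplied by a constant, and the 36-month EFS is 0.40 raised to that multiplier.

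| Multiplier | 36-month EFS | Overall alpha under the note |
|---|---|---|
| 1.00 | 40% | 2.77% |
| 0.95 | 42% | 2.68% |
| 0.90 | 44% | 2.60% |
| 0.85 | 46% | 2.52% |

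Using the 3-month delay where the event targets are not met, 47–48% gives 2.50% and 50% gives 2.43%.

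**Step 6: chance that no bound exists.** With an expected 397 or so interim events out of 780, the binomial SD is √(780 × 0.509 × 0.491) ≈ 14. The chance of more than 410 interim events under the null is about 18%.

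**Step 7: OS.** With the section 8.9 OS assumptions, the null gives about 244 and 283 deaths. The final p is 0.0233 under the note against 0.0221, and alpha is about 2.60%. This is rougher than the EFS result: the same model gives 213 and 249 deaths at a hazard ratio of 0.71, not the plan's 220 and 268. Scaling the hazards to reach 268 deaths gives about 263 and 304 null deaths and alpha of about 2.7%.

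**The case against.** The strongest reply is that the operative rule is already correct. The sentence written specifically for the final nominal alpha uses actual counts, the error-control argument repeats it, and following them gives exactly 2.50%. The note could be read as a provisional correlation used at the interim, when the final count is unknown, and superseded later. The 2.77% needs the note to prevail, no treatment effect, and a 36-month EFS of 40% in both arms. The shift in the hazard ratio bound is small (0.826 to 0.831). A ratio above 1 would be noticed and would push the statistician to the correct rule. Finally, the analysis is complete, so rewording cannot change the bound used.

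Much of this stands. The effect is modest and conditional, the sponsor may well have used the right rule, and the OS figures are weaker than the EFS ones. The provisional reading does not stand: nothing in the text labels it so, and the interim bound has no use for a correlation. The written plan still supports two different final thresholds for the primary endpoint.

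**Conclusion.** The concern holds. Section 8.8.1 states two incompatible correlation rules, and the one in the note after Table 29 is wrong for EFS whenever the final count differs from 410, and for OS whenever it differs from 268. The actual-count rule preserves 2.50%. Under the note, alpha is 2.77% at the null counts implied by the plan's own assumptions, and it falls to 2.50% or below once null 36-month EFS is about 47% or higher. The documents report no actual event counts, so this does not show that error was inflated. It shows that the text does not settle the bound on which the strong-control claim rests. It should be fixed.

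**What to change.** In the note after Table 29, replace the target by the observed number of final-analysis events as the denominator for the correlation. Keep the target denominator only for the interim alpha-spending fraction, where it is legitimate. State that the same rule applies to OS.

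Section 7.1.4.2 uses the words "Since completion of the final efficacy analysis", so the final analysis has already been done. The sSAP or clinical study report should therefore also record which correlation set the final EFS bound and, if OS was tested, the OS bound. We have not seen those documents and cannot say whether this is already recorded.

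The cost is one changed phrase and one line of record. The only statistical price is a slightly stricter final bound when events exceed the target: a hazard ratio of about 0.826 rather than 0.831 at 456 events. No data, sample size or timing changes.

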8.8.2 Multiplicity Control for Safety Analyses

There are multiple safety interim analyses planned in this study. The eDMC has responsibility for assessment of overall risk/benefit. When prompted by safety concerns, the eDMC can request corresponding efficacy data. eDMC review of efficacy data to assess the overall risk/benefit to study subjects will not require a multiplicity adjustment typically associated with a planned efficacy IA. However, to account for any multiplicity concerns raised by the eDMC review of unplanned efficacy data when prompted by safety concerns, a sensitivity analysis for OS adopting a conservative multiplicity adjustment will be pre-specified in the sSAP.

8.9 Sample Size and Power Calculations

The study will randomize approximately 780 subjects in a 1:1 ratio into the experimental arm of pembrolizumab in combination with CRT and the control arm of placebo in combination with CRT.

Power and IA calculations for EFS and OS were performed using the gsDesign R package,

Event-Free-Survival

The EFS hypothesis testing strategy was designed for $\alpha=0.025$ (one-sided) and power of 94.6% to detect a HR of 0.7 with 410 EFS events at the final analysis. The sample size was estimated based on the following assumptions:

- (1) true HR of 0.7;
- (2) the duration of EFS in the placebo in combination with CRT group is assumed to follow a piece-wise constant hazard exponential distribution with a cumulative EFS rate of 70% at 12 months, and 40% at 36 months;
- (3) an enrollment of 25 months, with accrual rates of 2 subjects per month for the first 2 months, 10 subjects per month for the next 2 months, ~24 subjects per month for the next 2 months, and ~38 subjects per month thereafter; and
- (4) a 10% cumulative dropout rate at 12 months in both treatment groups.

Overall Survival

At $\alpha=0.025$ (one-sided), the final OS hypothesis test yields 79% power to detect a HR of 0.71 with 268 deaths observed. The power was estimated based on the following assumptions:

- (1) true HR of 0.71;
- (2) the duration of OS in the placebo in combination with CRT group is assumed to follow a piece-wise constant hazard exponential distribution with a cumulative OS rate of 85% at 12 months, 65% at 36 months and 48% at 96 months;
- (3) the same enrollment assumption as used for EFS; and
- (4) a 3% cumulative dropout rate at 12 months in both treatment groups.

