12.9 Technical Note for the Piecewise Constant Hazard Exponential Survival

Given a set of time points, $0 = \tau_0 < \tau_1 < \dots < \tau_{m-1} < \tau_m$ the piecewise constant hazard function is defined as

$$\lambda(t) = \sum_{l=0}^m \lambda_l I_l(t) \quad \text{with } I_l(t) = \begin{cases} 1 & \text{if } \tau_l \leq t < \tau_{l+1} \\ 0 & \text{if elsewhere} \end{cases}$$

The exponential survival function is

$$S(t) = \exp\left(-\sum_{l=0}^m \lambda_l \int_0^t I_l(s) ds\right)$$

The survival function $S_i(t)$, for a given interval $\tau_i \leq t < \tau_{i+1}$, simplifies to

$$S_i(t) = \exp\left(-\sum_{l=0}^{i-1} \lambda_l (\tau_{l+1} - \tau_l) - \lambda_i (t - \tau_i)\right)$$

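### The OS inputs in section 8.9, with hazard changes at the stated months, give about 213 and 249 deaths instead of 220 and 268, so expected OS power is about 76–77%, not 79%

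*Combined protocol and SAP*

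**What the plan says.** Section 8.9 (Sample Size and Power Calculations) states that "the final OS hypothesis test yields 79% power to detect a HR of 0.71 with 268 deaths observed". It goes on: "The power was estimated based on the following assumptions". The inputs listed are a true HR of 0.71, a piecewise exponential control arm with "a cumulative OS rate of 85% at 12 months, 65% at 36 months and 48% at 96 months", the enrollment pattern used for EFS, and 3% cumulative dropout at 12 months in each arm.

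Section 8.8.1 says that the OS bounds assume "the number of OS events at IA and FA are 220 and 268, respectively". Table 30 dates these counts at months 48 and 60, with N = 780.

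The final analysis is triggered by EFS and follow-up (section 8.7.1, Table 27): "At least 410 EFS events have been observed and all subjects have been followed up for at least 35 months". On OS, section 8.8.1 adds: "The final OS analysis will occur at the same time as the final EFS analysis". If deaths differ from plan, "the same minimum spending approach as used for EFS will be implemented and the bounds will be adjusted accordingly".

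Appendix 12.9 sets out the model in general form ("the piecewise constant hazard function is defined as") but does not list the change points used for OS.

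**The concern.** The 79% is presented as the product of the listed inputs. Whether they deliver it depends on how many deaths they imply at month 60, because no rule holds the final OS test until 268 deaths have occurred. If the inputs imply fewer, the expected power of the key secondary endpoint is lower than stated. A reader weighing a non-significant OS result would then rely on a figure that cannot be rebuilt from the plan.

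**Working it through.** **Inputs (section 8.9; Table 30 for timing)**

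- Control OS hazards per month, with changes at 12 and 36: −ln(0.85)/12 = 0.01354; −ln(0.65/0.85)/24 = 0.01118; −ln(0.48/0.65)/60 = 0.00505. The pembrolizumab arm is multiplied by 0.71.
- Dropout hazard η = −ln(0.97)/12 = 0.00254.
- Accrual: 2, 2, 10, 10, 24 and 24 subjects in months 1–6 (72 in all), then about 38 a month for 19 months. Taken literally this totals 72 + 38 × 19 = 794. Scaling the last rate to (780 − 72)/19 = 37.3 gives 780.

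**Step 1: the stated power, given the stated deaths.** Lan-DeMets O'Brien-Fleming spending is α(t) = 2 − 2Φ(2.2414/√t), one-sided 0.025. The mean of the log-rank Z is −ln(HR) × √d/2.

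- At t = 220/268 = 0.821, the interim alpha is 0.0134 (Z = 2.215) and the final Z is 2.031. Table 30 has 2.2169 and 2.0305.
- The means are 0.3425 × √220/2 = 2.540 and 0.3425 × √268/2 = 2.803.
- Power is 79.2%. The stated 79% is reproduced, conditional on 268 deaths.

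**Step 2: check of the event-count method on EFS.** For a subject with follow-up u, the event probability is Σ P(j) × [λ(j)/(λ(j)+η)] × [1 − exp(−(λ(j)+η)Δ(j))]. Here P(j) is the probability of entering interval j with neither event nor dropout, and Δ(j) is the time spent in it. Averaging over entry times and arms gives expected events. The EFS inputs are hazards −ln(0.70)/12 = 0.02972, then −ln(0.40/0.70)/24 = 0.02332, HR 0.7, and dropout −ln(0.90)/12 = 0.00878. With 780 subjects they give 353.7 events at month 48 and 410.1 at month 60; Table 29 has 353 and 410. The bounds come out at 2.1517 and 2.0422, as in Table 29.

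**Step 3: the same calculation for OS**

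| Month | Control | Pembrolizumab | Total | Table 30 |
|---|---|---|---|---|
| 48 | 121.9 | 91.3 | 213.2 | 220 |
| 60 | 141.7 | 107.2 | 248.9 | 268 |

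The shortfall is 7 deaths (3%) at the interim and 19 (7%) at the final analysis. The inputs reach 268 at about month 70.

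**Step 4: power at those counts.** The final mean falls to 0.3425 × √248.9/2 = 2.702.

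- Bounds re-derived at 213.2/248.9: Z = 2.159 and 2.041, power 76.1%.
- The plan's minimum-spending rule, with interim spending at 213.2/268: Z = 2.258 and 2.001, final HR at bound 0.776 (Table 30: 0.78), power 76.6%.

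**Step 5: sensitivity, still with changes at 12 and 36** (power under minimum spending)

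| Variant | Deaths, interim/final | Power |
|---|---|---|
| Final analysis at month 63 (permitted delay) | 213/255 | 77.5% |
| Literal accrual, 794 subjects | 217/253 | 77.3% |
| No dropout | 221/261 | 78.3% |

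**Step 6: other change points that still meet all three OS rates** (780 subjects; power with bounds derived at those counts)

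| Change points (months) | Deaths, 48/60 | Power |
|---|---|---|
| 12 and 48 | 217.0/266.7 | 79.0% |
| 12 and 60 | 217.0/270.8 | 79.6% |
| 18 and 60 | 218.1/268.3 | 79.2% |
| 24 and 48 | 220.2/260.3 | 78.0% |

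With the first change at month 12 and the second anywhere scanned from 36 to 60, the month-48 count never exceeds 217.0. No pair of change points tried gave 220 and 268 together. Literal accrual with changes at 12 and 45 gives 220.8/268.1, but the same 794 subjects would make EFS 360.0/417.4, contradicting Table 29.

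**The case against.** The strongest reply is that section 8.9 gives months for survival rates, not for hazard changes, and Appendix 12.9 leaves the time points open. Changes at 12 and 48 fit all three rates and give essentially the stated power. The EFS check cannot settle this, because EFS has no rate after month 36 and its 12–36 hazard simply runs on. An elaborate five-piece curve with 780 subjects gives 220.1/267.1. The 220 may itself be a rounding of 0.82 × 268 = 219.8, and accrual, sample size and timing are all stated as approximate. OS did not size the trial, and the final efficacy analysis is already complete (Amendment 08).

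Much of this stands. The 268 cannot be called wrong under every curve, the month-48 gap is small, and no decision rule changes. But giving rates at 12, 36 and 96 months for a piecewise-constant hazard ordinarily places the breaks at those months. Each alternative needs a break, or a whole curve, that the plan does not state. A power said to follow from listed assumptions should be recoverable from them, and this one is not.

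**Conclusion.** The concern holds. With hazard changes at months 12 and 36, exponential dropout and accrual scaled to 780, the section 8.9 inputs give about 213 and 249 deaths, and expected OS power is 76.1–76.6% against the stated 79%. The month-60 shortfall carries the finding. It depends on the change points: either the counts are too high for the inputs as listed, or the curve behind them is undisclosed.

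The effect is modest. OS is tested only after EFS succeeds, its bounds adjust to the actual number of deaths, the final HR bound barely moves, and Type I error and EFS are untouched. What is affected is how OS power is reported and how an OS result is read.

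**What to change.** Add a note to section 8.9 and Table 30 that does one of two things:

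- restates the projected deaths as about 213 at month 48 and 249 at month 60, and expected OS power as about 76–77%; or
- if another control curve was used, such as the 12–36 month hazard carried beyond month 36, states that curve with its change points and shows that it yields 220 and 268.

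Leave 220/268 as the spending reference and keep the rule that adjusts the bounds to actual deaths, since the final efficacy analysis has been done. Sample size, bounds, Type I error and the EFS analysis do not change. The only cost is a stated OS power about 2.5–3 points less favourable, unless the sponsor documents a different curve.
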